Study Proposal & Statistical Analysis Plan

**Phase I/IIa Study of Pharmacokinetics and Safety of Atorvastatin in
Children with Coronary Artery Abnormalities Secondary to Kawasaki
Disease**

Investigators:

**[name], MAS
[name]**

May 20, 2016

NCT# 01431105

I. Study Overview

OVERALL OBJECTIVE

The goal of this study is to determine the safety, pharmacokinetics and activity of atorvastatin in children with acute Kawasaki disease (KD) and coronary artery abnormalities. The goal will be to find a treatment that could prevent or attenuate coronary artery damage in acute KD.

HYPOTHESIS

We postulate that atorvastatin will be safe in children ≥ 2 years old with acute KD.

STUDY TYPE

This is a Phase I/IIa dose escalation study

STUDY POPULATION

Children ≥ 2 years to 17 years with acute KD who have a Z-score ≥ 2.5 or aneurysm (≥ 1.5 x the adjacent segment) of one of the coronary arteries.

STUDY DURATION

4 years

PRIMARY OUTCOME

Safety of atorvastatin in the study population.

SECONDARY OUTCOMES

1. Pharmacokinetics of atorvastatin
2. Activity of atorvastatin
 - a. Biomarkers and measures of inflammation
 - b. Echocardiographic assessment of coronary artery abnormalities

II. Background & Significance

IIA. Significance:

KD, the most common cause of acquired heart disease in children in Western developed countries and Asia, is a systemic vasculitis of unknown etiology. In the United States, there are 5-6,000 new cases each year [1]. However, without a specific diagnostic test, the true burden of disease is unknown. At Rady Children's Hospital San Diego, we cared for over 90 new KD cases in 2010 and follow over 1,200 families in our outpatient KD Clinic (350 outpatient visits/yr.), of whom 9% developed aneurysms and 25% developed dilated coronary arteries. In Japan, the country of highest incidence ($>215/100,000$ children < 5 yrs), there are more than 12,000 new cases each year and rates continue to rise [2]. KD causes both a myocarditis and a vasculitis that damages the coronary arteries and other medium-sized muscular arteries [3, 4]. The major sequelae of aneurysms include thrombosis, late coronary artery stenosis, myocardial ischemia, myocardial infarction, and death [5, 6]. **Clearly, aneurysm prevention is a primary goal of treatment during the acute phase of the disease, which leads us to focus on treatment of patients with early signs of coronary artery abnormalities (CAAs) in this application.**

Intravenous immunoglobulin (IVIG) in combination with aspirin is the only approved therapy for KD and no clinical trials have focused on blocking the progression of coronary artery dilatation or aneurysm formation in the subset of KD patients who develop this complication. The major acute risk of aneurysm formation is thrombosis, which can be prevented with systemic anti-coagulation with warfarin or enoxaparin in addition to antiplatelet therapy with aspirin or clopidogrel in patients with large aneurysms

(>6 mm). However, there is no recommended therapy to halt the progression of arterial wall destruction and prevent aneurysm formation. In KD, CD8+ T-cells infiltrate the arterial wall and data from the [name] lab suggest that T-cell regulation is a key factor in reducing the acute inflammation[7, 8] **The proposed studies will determine if atorvastatin is safe to use in young children and has demonstrable anti-inflammatory activity at a well-tolerated dose so that future studies can address the efficacy of atorvastatin in attenuating vascular wall damage and preventing aneurysms in KD patients.**

IIB. Importance of the problem

Once aneurysms have formed, there is no way to turn back the biologic clock and undo them. The transmural inflammation destroys the normal architecture and even in children who remodel the aneurysm to form a more normal lumen, the vessel is never functionally normal again. The remodeled segment cannot dilate normally during increased myocardial oxygen demand and thus serves as a functional stenosis. It has been estimated that there are currently over 24,000 young adults in the United States with a history of KD, including over 8,000 with a history of coronary artery abnormalities. Without a new therapeutic approach this number is expected to grow by 1,400 individuals each year [6]. A recent study found that over 5% of all young adults (<40 years) evaluated by cardiac catheterization for suspected myocardial ischemia have aneurysms compatible with antecedent KD[9].

IIC. Validity of the approach

A Phase I/IIa trial will generate sufficient data to determine if a full-scale Phase III trial is warranted. The trial will also establish if the anti-inflammatory effects of statins can be measured in children with an acute vasculitis.

IID. Critical barriers to improving care

Barriers to improving treatment for children with KD include the lack of a validated predictive score to identify those children at highest risk of aneurysm formation and lack of a therapeutic intervention that can prevent progression of CAAs once they have been detected.

IIE. Potential to effect change in clinical practice

The current clinical practice is to give every patient the same standard therapy (IVIg 2g/kg with aspirin 80-100mg/kg) and to monitor for CAA. The mechanism of action of this immunomodulatory therapy remains unknown, but is being addressed by other research by the PI in collaboration with [name] (RO1 HL103536 and RO1 FD003514). In the unfortunate child who carries the genetic risk for CAA, no intervention to modify vessel wall inflammation is currently recommended [10].

In a recent article entitled “Mining for therapeutic gold”, Director of the NIH, [name], stated that “drug repurposing” should be a strategy “to translate research into clinically useful products” [11]. Our goal is to translate our findings on the role of matrix metalloproteinases (MMPs), T-cells, and myofibroblasts in KD aneurysm formation and “repurpose” the drug atorvastatin to test the hypothesis that the pleiotropic anti-inflammatory properties of this drug will prevent or attenuate coronary artery aneurysms in children with KD.

IV. Specific Aims

Specific Aim 1 will test the hypothesis that a 6-week course of atorvastatin will be safe and well-tolerated in children with KD and early CAAs.

The safety of atorvastatin will be assessed. A dose escalation design will be used to find a dose in subjects that is tolerated with limited side effects.

V. Human subjects

VA. Inclusion criteria:

1. Age \geq 2 years to 17 years old
2. Meets clinical criteria for KD according to AHA guidelines (Table 2): Fever ($T \geq 38.0^{\circ}\text{C}$ or 100.4°C by oral or rectal route; if measured by a non-core route (i.e. Axillary, ear, temporal artery), then add 0.5°C to temperature; by history acceptable) \geq 3 days and \geq 2 clinical criteria with LAD/RCA z-score \geq 2.5 or an aneurysm (\geq 1.5 x the adjacent segment) of one of the coronary arteries
3. Patient presents within the first 20 days after fever onset
4. Parent or legal guardian able and willing to provide informed consent and subject willing and able to provide assent when appropriate.
5. Post-menarchal females: Negative pregnancy test at screening and willing to use two forms of contraception during the study
6. Males engaging in sexual activity that could lead to pregnancy must use a condom.

VB. Exclusion Criteria:

1. Use of a statin, fibrate, or niacin within the 3 months prior to enrollment
2. Have any chronic disease, except asthma, atopic dermatitis, autism or controlled seizure disorder
3. Screening creatine phosphokinase (CK) \geq 3x upper limit of normal for age
4. Patient taking a CYP3A4 inhibitor (i.e. cyclosporine, clarithromycin or doxycycline) in the last 7 days
5. Patient has a history of allergy to atorvastatin or its derivatives

VC. Data Collection: The following data will be recorded for all patients:

1. Demographic data:

- Patient's age at KD onset, sex, self-reported ethnicity of each biologic parent

2. Clinical data:

- Physical findings confirming the KD case definition (**Table 2**)[10]
- Illness day at study entry
- Response to IVIG (IVIG-resistance will be defined as persistent or recrudescing fever ($T \geq 38.0^{\circ}\text{C}$ rectally) \geq 36 h and $<$ 7d following the end of the IVIG infusion (2g/kg)[14].) -
- Name, dose and indication of concomitant medications taken from enrollment until study completed
- Complete blood count, C-reactive protein (CRP), high sensitivity CRP (hsCRP), erythrocyte sedimentation (ESR), aspartate aminotransferase (AST), ALT, and GGT at baseline, 2 weeks and 6 weeks
- CK and fasting lipid panel at baseline (after enrollment), 2 weeks and 6 weeks

VI. Statistical analyses

Incidence rates of adverse events and the proportion of subjects prematurely withdrawn from the study due to adverse events was compiled. For continuous variables, the Kruskal Wallis Test was performed to compare the four dose levels. For categorical variables, Fisher's Exact Test was performed. Statistical analyses were performed using the statistical software R (version 3.4.4) (<http://www.r-project.org>). Analyses were performed following the intent-to-treat principle. No adjustments for multiple comparisons were made for secondary analyses, and a p-value of 0.05 was considered statistically significant.

VII. Literature Cited

1. Kaneko, K., et al., *Prediction of the Risk of Coronary Arterial Lesions in Kawasaki Disease by Brain Natriuretic Peptide*. *Pediatr Cardiol*.
2. Nakamura, Y., et al., *Epidemiologic Features of Kawasaki Disease in Japan: Results of the 2007-2008 Nationwide Survey*. *J Epidemiol*, 2010.

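### The echocardiographic outcome should also be reported by coronary state at entry: eligibility mixes dilation with established aneurysm, and Section VI names only unstratified dose-level comparisons

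*Combined protocol and SAP*

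**What the plan says.** **Population.** The Study Overview admits children "who have a Z-score ≥ 2.5 or aneurysm (≥ 1.5 x the adjacent segment) of one of the coronary arteries". Section VA, criterion 2, has the same two routes and specifies LAD/RCA for the Z-score. Neither place sets a cap or a stratum for aneurysm at entry.

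**Outcome.** Secondary outcome 2b is a single line: "Echocardiographic assessment of coronary artery abnormalities". It gives no metric, time point or direction of benefit.

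**Purpose.** The Overview says "The goal will be to find a treatment that could prevent or attenuate coronary artery damage in acute KD". Section IIA explains that aneurysm prevention matters most in the acute phase, "which leads us to focus on treatment of patients with early signs of coronary artery abnormalities (CAAs) in this application". It then describes the trial as a test of safety and anti-inflammatory activity, "so that future studies can address the efficacy of atorvastatin in attenuating vascular wall damage and preventing aneurysms in KD patients".

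**Biology.** Section IIB states: "Once aneurysms have formed, there is no way to turn back the biologic clock and undo them". On remodelling it adds that "even in children who remodel the aneurysm to form a more normal lumen, the vessel is never functionally normal again".

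**Analysis.** Section VI applies Kruskal-Wallis to continuous variables, for the comparison of the four dose levels, and Fisher's exact test to categorical ones. It names no stratification, covariate or subgroup. Specific Aim 1 describes dose escalation; random allocation between levels is not mentioned.

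**The concern.** The two entry states do not have the same possible outcomes. A child with dilation only can progress to a first aneurysm or not. A child who enters with an aneurysm can show enlargement, no change or a shrinking lumen, and the plan itself says that the last of these is not a return to normal function.

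Two problems follow if the tests in Section VI are applied to the echocardiographic outcome as they stand:

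1. **Cohort mix.** In a dose-escalation study, children join the level that is open when they present. Levels may therefore differ in their share of aneurysm children, and a difference in echocardiographic change between levels may reflect that share instead of dose.
2. **Mixed meaning.** An average change in lumen size or Z-score over all children may be produced by remodelling in the aneurysm children alone. A reader would take it as activity against early disease.

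Echocardiography is one of the two activity measures listed, and Section IIC expects the trial to inform whether Phase III is warranted. A misread echocardiographic signal could therefore matter, although Section IIC ties no decision rule to it.

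**Working it through.** The plan states no sample size, echocardiographic rate or effect size, so there is no figure to reproduce. What follows shows the possible scale only.

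**Inputs**
- Clinic rates, Section IIA: 9% developed aneurysms and 25% developed dilated arteries.
- Four dose levels, Section VI.
- Six children per level: assumed.
- Z-score fall of 1 to 3 units in children with an aneurysm at entry, and none in the others: assumed.

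**Step 1: aneurysm share among eligible children**
- If the 9% and 25% groups are separate: 9/(9 + 25) = 9/34 = 26%.
- If the 9% lie within the 25%: 9/25 = 36%.

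These rates describe whether a lesion ever developed in the clinic's patients, so on timing they run high for status at entry. Age limits, the 20-day window and consent could move the enrolled share either way. The range is an assumption, not a bound.

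**Step 2: variation in mix between levels.** Let s be the share.
- Expected aneurysm children per level: 6 × 0.265 = 1.6, or 6 × 0.36 = 2.2. This leaves about 4.4 or 3.8 without an aneurysm.
- Chance that a given level has none, (1 − s)^6: 0.735^6 = 0.158, or 0.64^6 = 0.069.
- Chance that at least one of four levels has none, 1 − [1 − (1 − s)^6]^4: 1 − 0.842^4 = 0.50, or 1 − 0.931^4 = 0.25.
- Chance that a given level has three or more, from Binomial(6, s): 0.19, or 0.37.

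**Step 3: effect on a dose contrast.** With fall d in aneurysm children only, two levels holding k and m of them differ in mean change by d(k − m)/6. For k = 3 and m = 0 this is 0.5d, that is 0.5 to 1.5 Z-score units, with no effect of dose at all.

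**Step 4: effect on the pooled mean.** The pooled fall is s × d:

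| Fall in aneurysm children | s = 26% | s = 36% |
|---|---|---|
| 1 | 0.26 | 0.36 |
| 2 | 0.53 | 0.72 |
| 3 | 0.79 | 1.08 |

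In every cell the children without an aneurysm at entry have not changed.

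**What steps 2 and 3 do not show.** If the mix varies between levels by chance alone, the unstratified tests keep their nominal error rate. The cost is noise and a result that is hard to interpret. The tests would be biased only if the mix drifted over the four-year study alongside the dose, which a sequential design without randomisation does not prevent.

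**The case against.** The case on the other side is substantial, and much of it stands.

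- **Pooling as the reason that prevention cannot be shown.** A reader might infer this; the documents do not support it. Children without an aneurysm at entry remain informative. The larger obstacle is that the only comparison described is between dose levels, with no untreated control, and a split by entry lesion does not change that. The plan also aims at attenuation as well as prevention, and Section IIA leaves efficacy to later studies.
- **The plan as counting remodelling as benefit.** This is also tempting, but no metric or direction of benefit is given. It is a risk if lumen size or Z-score is used, not something that the plan says. Pooling, too, is inferred from the absence of any split.
- **Regression as worthless.** Section IIB says that a remodelled vessel is not functionally normal. It does not say that a smaller lumen has no value, and Section IIA treats aneurysm size as relevant to thrombosis. A rule that regression may never count as activity would go beyond the text. Nor is a new aneurysm ruled out in a child who has one already, since eligibility needs a lesion in only one artery.
- **No echocardiogram in the Section VC list.** This is weak evidence. The available text passes from Section II to Section IV, and Table 2 is cited but not present, so a schedule may exist elsewhere. The point does not rely on it.
- **Subgroup size.** About four children per level without an aneurysm, under the assumed cohort size, cannot carry a test.

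What survives is narrower: the plan admits two states that it describes as biologically different and names no analysis that keeps them apart.

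**Conclusion.** The point holds as an inexpensive improvement to a secondary outcome and is of minor severity. It rests on three things in the documents: mixed eligibility, the plan's own statement that a more normal lumen is not normal function, and unstratified comparisons across levels for which no randomisation is described. Together these leave any overall echocardiographic result open to two readings.

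The size is illustrative. The 26% to 36% share is borrowed from clinic patients, and the six children per level and the Z-score falls are assumed. Under those inputs, imbalance between levels would be common and the pooled change from remodelling alone could reach about one Z-score unit. Nothing here shows that such a result would occur, and the primary safety outcome is untouched.

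**What to change.** Leave eligibility unchanged. In Section VI, keep the overall echocardiographic result and add a report by coronary state at entry, taken from the qualifying echocardiogram with the plan's own criterion of 1.5 times the adjacent segment:

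- **No aneurysm at entry:** number with a new aneurysm, and maximum LAD/RCA Z-score after entry, by dose level.
- **Aneurysm at entry:** change in lesion size by dose level, with enlargement and regression both shown, and regression not described as recovery.
- **Each level:** the number of children in each entry state.
- **Interpretation:** a sentence stating that, with no untreated control described, neither subgroup supports a claim of prevention and the results are descriptive activity data.

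The cost is a few lines of text and one more set of tables from measurements already needed for eligibility and for outcome 2b. The drawback is very small cells, which is why the subgroup results should be listed rather than tested. Section VI is written in the past tense. If the analysis has already been done, the breakdown is still useful but should be labelled post hoc.

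### Section VI reports the primary safety outcome as adverse event rates with no stated confidence interval, and its between-dose tests cannot bound the rate at any dose (minor)

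*Combined protocol and SAP*

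**What the plan says.** Section I (Primary Outcome) gives "Safety of atorvastatin in the study population", and Study Type reads "This is a Phase I/IIa dose escalation study". Section IV opens with "Specific Aim 1 will test the hypothesis that a 6-week course of atorvastatin will be safe and well-tolerated in children with KD" and early coronary abnormalities, then continues in softer terms: "The safety of atorvastatin will be assessed" and "A dose escalation design will be used to find a dose in subjects that is tolerated with limited side effects".

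Two statements in the background set out what the results are for. Section IIA says "The proposed studies will determine if atorvastatin is safe to use in young children". Section IIC says "A Phase I/IIa trial will generate sufficient data to determine if a full-scale Phase III trial is warranted".

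The analysis is in Section VI. On safety it says "Incidence rates of adverse events and the proportion of subjects prematurely withdrawn from the study due to adverse events was compiled". It then names Kruskal-Wallis for continuous variables, to compare the four dose levels, and Fisher's exact test for categorical variables, without restating the groups. The significance level is 0.05. Section VI states no confidence interval, upper limit or reference rate, and it does not say that numerators and denominators will be shown by dose.

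**The concern.** The question the study sets itself is absolute: is the drug safe at a given dose? The planned inferential tools are relative, because they ask whether dose levels differ from each other. Four doses with the same high event rate and four doses with the same low rate look alike to such a test.

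That leaves the compiled proportion as the only evidence on the absolute rate, and it comes without a measure of its uncertainty. A reported 0% from a handful of children and a reported 0% from several dozen read the same on the page but leave very different true rates open. The statements in Sections IIA and IIC, on safety and on going to Phase III, depend on that difference.

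**Working it through.** The plan states no sample size, event count or safety threshold, so there is no figure of its own to reproduce. The check has three parts. Every group size below is an assumption, except the minimum sizes in step 2, which assume none.

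**1. Can the between-dose test say anything about the absolute rate?** Take an assumed 6 children at each of four doses, with the same count k at every dose. Given the total, the probability of a table is the product of C(6, kᵢ) over the four doses, divided by C(24, total). Equal counts give the most probable table, so Fisher's p-value is 1.00 whatever k is.

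| Events at each dose | Fisher p | Pooled rate | Exact 95% CI, pooled |
|---|---|---|---|
| 0/6 | 1.00 | 0% | 0 to 14.2% |
| 1/6 | 1.00 | 16.7% | 4.7 to 37.4% |
| 3/6 | 1.00 | 50% | 29.1 to 70.9% |
| 5/6 | 1.00 | 83.3% | 62.6 to 95.3% |

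The p-value is the same in all four rows. Only the interval tells them apart.

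**2. What does zero events at a dose exclude?** For 0 events in n children the exact (Clopper-Pearson) two-sided 95% upper limit is U = 1 − 0.025^(1/n). The one-sided 95% limit is 1 − 0.05^(1/n). To bring U below a rate p requires n > ln(0.025)/ln(1 − p), or ln(0.05)/ln(1 − p) for the one-sided limit.

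- p = 20%, two-sided: 3.689/0.2231 = 16.5, so n = 17. Check: n = 16 gives 20.6%, n = 17 gives 19.5%.
- p = 10%, two-sided: 3.689/0.1054 = 35.01, so n = 36. Check: n = 35 gives 10.003%, n = 36 gives 9.7%.
- p = 20%, one-sided: 2.996/0.2231 = 13.4, so n = 14.
- p = 10%, one-sided: 2.996/0.1054 = 28.4, so n = 29.

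The 10% and 20% are yardsticks for precision and are not proposed safety limits.

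**3. What would this look like at plausible group sizes (assumed)?** Two-sided upper limits for zero events:

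| n | 4 | 6 | 8 | 10 | 12 |
|---|---|---|---|---|---|
| Upper limit | 60% | 46% | 37% | 31% | 26% |

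At n = 6 the one-sided limit is 39%. In the other direction, six children would show no event with probability 0.9⁶ = 53% if the true rate were 10%, and 0.8⁶ = 26% if it were 20%.

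Steps 2 and 3 suit withdrawals or other infrequent events. The proportion of children with any adverse event may be well above zero in an acute vasculitis treated with IVIG and aspirin, and there the interval is wide on both sides: an assumed 4/6 gives 22% to 96%.

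**The case against.** The strongest reply is that nothing here is wrong for a study of this type. Phase I/IIa safety reporting is normally descriptive, and a reader given n and N can compute the interval. That stands as to validity. It does not remove the gap, because Section VI does not promise n and N by dose.

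Four stronger readings are tempting, and the documents do not support them.

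- *A reader might infer that Aim 1 promises a formal test which the plan then omits.* The document uses the phrase loosely. Section IIE uses the same hypothesis-testing idiom about preventing aneurysms, a question that Section IIA leaves to future studies. The sentence right after Aim 1 says only "The safety of atorvastatin will be assessed". The wording is a matter of preference.
- *A reader might infer that nothing in the trial bounds the event rate.* The text supports this only for Section VI. An escalation rule with an event limit would bound the rate implicitly. None appears, but the document seems abridged: the numbering passes from II to IV, a cited Table 2 is absent, and the dose levels are not listed.
- *A reader might take the zero-event limits as applying to adverse events generally.* They apply only where zero is a realistic count.
- *A reader might expect an interval to make the safety question decidable.* It would not, because the plan names no acceptable rate. It shows how much is left open and no more.

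The choice between one-sided and two-sided limits is also open. It moves the thresholds from 17 and 36 to 14 and 29, and does not change the conclusion.

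**Conclusion.** The concern holds as a minor point about reporting precision. Section VI summarises the primary outcome with no stated interval, and its tests compare groups, so neither shows how large a rate the data leave open at a dose. This conclusion rests on the text of Section VI and needs no assumption about sample size. The reading of Fisher's test as a between-dose comparison is by context, but under any grouping it would not bound an absolute rate.

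The size depends on the number per dose, which is not given. The minimum sizes of 17 and 36 children hold without assuming one. The 46% figure rests on an assumed six per dose. The analysis is not invalid, and no result is shown to be wrong.

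**What to change.** Keep the sentence on incidence rates in Section VI, since it may cover rates by event type that a per-child proportion would lose. Add after it:

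> For each dose level, and pooled as an additional summary, the number and proportion of children with at least one adverse event, and of children withdrawn for an adverse event, are reported as n/N with an exact (Clopper-Pearson) two-sided 95% confidence interval.

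Optionally, reword Aim 1 so that it speaks of estimating safety and tolerability instead of testing a hypothesis.

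The cost is one sentence and two columns (n/N and interval) in the adverse event table, with no new data and no new test. The downside is that wide intervals will make the safety statement less favourable. Section VI is written in the past tense, so if the data have already been analysed, the intervals should be labelled as added after analysis.

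### Section VI leaves unspecified how baseline enters the inflammation-marker comparisons across dose levels, and the one test it names for continuous variables cannot adjust for baseline

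*Combined protocol and SAP*

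**What the plan says.** The Study Overview lists, under activity of atorvastatin as a secondary outcome, "Biomarkers and measures of inflammation". It gives neither a scale (value or change) nor a time point.

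Section IIC sets the ambition: "The trial will also establish if the anti-inflammatory effects of statins can be measured in children with an acute vasculitis".

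Section VC records "C-reactive protein (CRP), high sensitivity CRP (hsCRP), erythrocyte sedimentation (ESR), aspartate aminotransferase (AST), ALT, and GGT at baseline, 2 weeks and 6 weeks", in a list that begins with the complete blood count. It also records "Illness day at study entry".

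Section VI names one test for continuous data: "For continuous variables, the Kruskal Wallis Test was performed to compare the four dose levels". No covariate, response or visit is given there or elsewhere.

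On how patients reach a dose, Section IV says: "A dose escalation design will be used to find a dose in subjects that is tolerated with limited side effects". No randomisation to dose is described.

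**The concern.** Kruskal-Wallis compares groups on a single number per patient and takes no covariate. With markers measured at entry and at two later visits, that number could be the week-2 value, the week-6 value, or the change to either. The choice affects power, and which choice is better depends on the correlation between baseline and follow-up. A baseline-adjusted analysis largely avoids having to guess that correlation, and the data for it are already collected.

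Two features make baseline relevant here. Section VA admits patients at any time up to 20 days after fever onset, so marker levels at entry may be widely spread. The dose cohorts come from escalation, so they may also differ at baseline.

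At stake is how well the trial can detect a difference between doses on its secondary activity markers. The documents do not say that a between-dose difference is how activity will be judged, but Kruskal-Wallis is the only test named for a continuous marker.

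**Working it through.** The plan states no figure that could be reproduced. Everything below uses assumed inputs.

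**Inputs from the documents:** four dose levels; Kruskal-Wallis; significance level 0.05 (Section VI); baseline and two follow-up measurements (Section VC).

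**Assumed inputs:** equal groups of n = 6, 8 or 10 per dose; normal values with SD 1; shifts of 0, 0.4, 0.8 and 1.2 SD across doses; baseline to follow-up correlation ρ of 0, 0.3, 0.5 or 0.7.

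**Step 1: variance relative to a follow-up-only comparison.** Change from baseline: 2(1 − ρ). Baseline-adjusted: 1 − ρ².

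| ρ | follow-up | change | adjusted |
|---|---|---|---|
| 0 | 1 | 2.00 | 1.00 |
| 0.3 | 1 | 1.40 | 0.91 |
| 0.5 | 1 | 1.00 | 0.75 |
| 0.7 | 1 | 0.60 | 0.51 |

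Follow-up is better than change below ρ = 0.5 and worse above it. Adjustment is never worse than either, apart from the degree of freedom it uses.

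**Step 2: simulated power, nominal 5% tests** (100,000 replicates per cell). Entries are % at n = 6/8/10. KW is Kruskal-Wallis; rank ANCOVA is Quade's method.

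| ρ | KW follow-up | KW change | rank ANCOVA |
|---|---|---|---|
| 0 | 30/44/56 | 16/22/29 | 34/46/57 |
| 0.3 | 30/44/56 | 22/32/41 | 36/49/61 |
| 0.5 | 30/44/56 | 30/44/56 | 41/57/69 |
| 0.7 | 30/44/56 | 50/68/80 | 55/72/84 |

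**Step 3: remove the size difference.** Under the null, Kruskal-Wallis with the chi-square cut-off rejects 4.1–4.5% of the time and rank ANCOVA 5.0–5.5%, so part of the gain in Step 2 is an artefact. With both tests held at 5% by simulated cut-offs, the gain of rank ANCOVA in power points (good to about 1 point) is:

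| ρ | over better KW version | over worse KW version |
|---|---|---|
| 0 | −1.6 to −1.1 | 14–26 |
| 0.3 | 0.6–2.3 | 9–17 |
| 0.5 | 6.4–10.5 | 7–11 |
| 0.7 | 0.5–2.0 | 20–26 |

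If log values are normal, parametric ANCOVA gains 3–5, 10–15 and 7–8 points over the better size-matched version at ρ = 0.3, 0.5 and 0.7.

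**Step 4: false positives when cohorts differ and the drug does nothing.** One cohort is shifted by 1 SD; ρ = 0.3 to 0.7; n = 6 to 10; nominal 5%.

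| Model | KW follow-up | KW change | rank ANCOVA |
|---|---|---|---|
| Follow-up depends only on observed baseline | 5.8–26.4% | 6.9–19.7% | 4.4–4.6% |
| Persistent difference in true level, measurement error at both visits | 27.7–52.9% | 3.9–4.6% | 7.8–22.7% |

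No method stays near 5% under both models. If instead follow-up depends on illness day (assumed 0.3 or 0.5 SD per SD) and one cohort enters 1 SD later, rank ANCOVA on baseline alone rejects 7.6–26.1% of the time, against 5.5–15.2% for follow-up and 5.7–23.0% for change. Baseline adjustment is not a general safeguard against confounding.

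**The case against.** A reader might infer that the planned comparisons ignore baseline. The documents do not support that. Since no response is named, Kruskal-Wallis may have been run on change from baseline, which uses baseline. What the text shows is that its use is unspecified.

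A reader might also infer that the dose cohorts were unbalanced, or that adjustment would make the comparison safe. The documents contain no cohort data. In Step 4, Kruskal-Wallis on change holds its level under a persistent cohort difference while rank ANCOVA does not. This objection stands: the case for adjustment is precision, and change from baseline should not be relegated.

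The gain over the better unadjusted version is negligible except near a correlation of 0.5. This stands too. The larger losses arise only if the worse version was used, which nothing in the documents shows. But the documents give no correlation from which to tell which version that is.

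Under the assumed linear dose effect, a trend test gains more than adjustment does. At n = 8, an unadjusted rank trend test on follow-up has about 66% power at correlations 0.3 and 0.5, against 49% and 57% for rank ANCOVA; on change at 0.7 it has about 86%, against 72%. That is correct, but it is a separate choice (ordered or omnibus alternative). It neither settles the response and visit nor rules out adjustment.

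Finally, the outcome is secondary, and Section VI is written in the past tense, so pre-specification may no longer be possible. Both limit the weight of the point.

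**Conclusion.** The point holds in limited form. Section VI names only an unadjusted test, with no response or visit, so how the collected baseline values enter the inflammation-marker comparisons is unspecified, and the named test cannot adjust for them.

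Its size rests on the assumed group sizes, correlations, normality and 1.2 SD shift, none of which comes from the documents. On those assumptions, baseline adjustment roughly matches the better unadjusted version at most correlations, beats it materially near 0.5, and protects against having chosen the worse one. A smaller effect does not change the pattern: with a 0.8 SD shift the nominal gain over the better version is 3–4, 6–8 and 4–5 points at correlations 0.3, 0.5 and 0.7, before any size correction.

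This is a worthwhile, low-cost improvement to a secondary analysis. It does not bear on adverse-event incidence or the primary safety conclusion. CK, liver enzymes and lipids fall under the same sentence but were not examined here.

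**What to change.** For blood count, CRP, hsCRP and ESR, state the scale and visit. Compare the week-2 and week-6 values by dose with rank ANCOVA, or ANCOVA on the log scale, adjusted for that marker's own baseline. Beside it, with equal prominence, report Kruskal-Wallis on change from baseline as a sensitivity analysis, since neither method controls false positives under every form of cohort difference.

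Tabulate baseline markers and illness day at entry by dose. State that the adjustment is for precision and does not remove confounding. Illness day may be added as a covariate; if it is not prognostic, this costs about 1 to 3 points of power. Name the response and visit for the other continuous laboratory values as well.

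The cost is SAP wording, a little extra analysis, one degree of freedom, and about 1 to 2 points of power if baseline is uncorrelated with follow-up. No new data are needed. If results are already known, label the adjusted analysis post hoc.
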